9.10.2 Independent Ethics Committee or Institutional Review Board

This multicenter, prospective cohort study with a medical device is classified as “Sonstige Klinische Prüfung” (other clinical study) as per Article 82 Regulation (EU) 2017/745 /§3 No. 4 MPDG. The medical device used in this study for physiological monitoring will be used modified to its CE marking with the addition of temperature monitoring capabilities. Prior to commencement of the study at a given site, the protocol will be submitted together with its associated documents to the responsible Independent Ethics Committee (IEC)/Institutional Review Board (IRB) for its opinion.

The study must not start at a site before the Sponsor has obtained written confirmation of a favorable opinion from the concerned IEC/IRB in accordance to §47 (2) No. 1 and §52 Section 1 MPDG.

The written evidence of the favorable opinion from the concerned IEC/IRB will be filed in the trial master file and a copy will be sent to the Investigator. The written evidence should clearly identify the study, the protocol version, and the Informed Consent Form version reviewed. In addition, the IEC/IRB will be asked to provide documentation of the date of the meeting at which the study was discussed, and of the members and voting members present at the meeting.

In accordance with § 54 MPDG, all changes to the protocol and any applicable documentation will be notified to the responsible IEC/IRB immediately. In case of substantial changes, the responsible IEC/IRB will be asked for favorable opinion in accordance with § 55 MPDG. Substantial changes will only be implemented, if the responsible IEC/IRB issues a favorable opinion or if the responsible IEC/IRB issues no rejection notice within 38 days after confirmation of a formally complete application.

In case of temporary suspension or premature termination of the study, the responsible IRB/IEC will be notified within 15 days with indications of the reasons. If the temporary suspension or premature termination are performed out of security reasons, the responsible IRB/IEC will be notified within 24 hours in accordance with §64 MPDG.

9.10.3 Monitoring

A CRO will perform monitoring according to the study's Monitoring Plan. Investigators need to ensure that the Monitor has access to relevant documents during monitoring visits and that they and/or relevant site staff members are available to discuss any issues that may arise.

Recruitment rates and exacerbation frequency in the COPD study population will be reviewed in 2-week intervals to compare against assumptions and allow for timely adjustments of the study protocol and conducting sites to reach the projected minimum number of moderate or severe exacerbations (n=18). Participants will be instructed to inform any physician outside of this study of their participation in this study and the need to inform the respective PI on relevant medical events and exacerbations.

The study monitor will send monitoring reports to the Sponsor.

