Specifically, this study aims at predicting 2 target outcomes: acute exacerbations of COPD (AECOPDs) as defined by the GOLD initiative, and the CAT score as a proxy for patients' disease status. The start of an exacerbation within a patient, regardless of how many exacerbations the patient may have experienced before, will be predicted based on sensor data preceding the

exacerbation, and using basic covariates as well. For type of exacerbations, the severe and moderate exacerbations are considered as our main target as these are linked to the need of urgent medical intervention and will predict those as a group, but also separately (distinguish by type), if possible. Mild exacerbations, the relevance of which is currently a subject of investigation in the field, will also be explored.

For the CAT score, the aim is to predict the total score (max = 40) from the sensor data, and changes in the CAT score of ≥ 2 based on the MCID. With this approach, it is aimed to use the model built on sensor data as an objective means to reflect patients' disease status. While for the prediction of exacerbations the aim is to predict them as early as possible, i.e. days before an exacerbation, for the CAT/disease status prediction the aim is to reflect the daily status.

CCI

This study is exploratory in nature and any predictive models will need to be validated in future studies. A future remote patient monitoring (RPM) solution for patients with COPD built on these models will have 2 prime utilities: First, ameliorating or preventing exacerbations and their negative sequelae by early treatment intervention and second, to provide physicians and patients with a highly granular and precise view on the current disease status and past changes. Such information can be used by the treating physician to optimize therapeutic regimens and by the patients to accompany and optimize lifestyle changes. By using a multimodal sensor approach we intend to increase the accuracy of our predictive models beyond what has been described in the literature and thereby increase their clinical utility.

8 Research Question and Objectives

The aim of the study is to investigate the correlation of real-world sensor-derived biometric data obtained via a wearable device with clinical parameters and PROs for monitoring disease activity and predicting exacerbations for patients with COPD.

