9.5 Study Size

Sample size calculation is based on the second part of the primary objective, especially on predicting exacerbations of a severe or moderate type as outcome.

Assuming a desirable sensitivity and specificity of 0.85 for our algorithm and requiring that the lower 95% confidence limit should be at least 0.50 (with a probability of 0.95) for this exploratory approach, the number of observed exacerbation events needed is 18 ([Flahault 2005](#)).

Assuming that patients with COPD within our eligibility criteria (GOLD stage II-IV with a history of at least 2 moderate and/or severe exacerbations within any 12 month period within the last 3 years and at least 1 moderate or severe exacerbation within the last 12 months) show a frequency of 2 moderate or severe exacerbations per year, participants with COPD will have 0.5 events in 3 months (the in-study time). Further assuming that event occurrence over 3 months for every individual participant follows a Poisson distribution with parameter $\lambda = 0.5$, the number of events in the overall study population is also Poisson distributed and the corresponding parameter is the sum of individual parameters λ . Calculations show that a λ of 30 is needed to reach an upper cumulative distribution probability of 0.99 for observing at least 18 exacerbations. Therefore, 60 participants are needed to observe at least 18 exacerbation events within the 3-month observation period.

The events of interest in the context of the present study are COPD exacerbations (severe or moderate), exactly the onset of an exacerbation. For building the binary classifier predictive models we also require “no exacerbation” events. We will sample such events randomly from periods with no exacerbations, avoiding 2 weeks before and after an exacerbation.

Considering a drop-out rate of 10%, the estimated number is 67 participants with COPD that need to be included in this study.

This recruitment number is also in good agreement with published studies with regards to the ability to build predictive models for exacerbations. Studies with similar recruitment numbers ([Yañez 2012](#)) have been able to predict exacerbations based on single parameters studied. Strong features can compensate for low numbers in COPD machine learning model building as shown in

[Al Rajeh 2020](#), and using several features improves the accuracy of predictive models as seen in [Jensen 2012](#).

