9.9 Limitations of the Research Methods

- The data is collected from a very limited number of study sites in Germany. Hence the study population may not be representative of the population of patients with COPD. In addition, the fact that participation in the study requires cognitive capabilities to use applications and devices used for data collection in the study may cause selection bias towards a younger age group.
- Daily averages will be calculated to represent continuous measurements each day. There may be additional information encoded in smaller time periods (hour by hour or minute by minute) data or through defining bouts of activity.
- Some of the outcomes are based on subjective self-assessment e.g. COPD symptoms and health status will be assessed by the CAT score. In validation studies, the CAT score has been shown to be a valid and reliable tool to assess perceived health status (Jones 2013), though validity of the online version remains to be proven.
- The number of observed exacerbations will be low, and predictive models will need to be refined and validated in a larger population.

- Severe and moderate AECOPDs will likely be encountered in only ~40% of the participants with COPD. This may impact the generalizability of predictive models for AECOPDs.
- This study is a national study in Germany and will only recruit patients with sufficient proficiency in the German language. It is therefore impossible to assess potential bias in the gathered data and conclusions with regards to language, ethnicity, cultural background, country of origin, and social factors not encountered in the study population. This refers both to PROs and the interpretation of sensor data. Future studies will need to study these potential biases in a multinational setting.
- Mild exacerbations are captured via the labelling section in the patient facing application as “additional medication used” (self-reporting). Therefore, the capture of mild exacerbations depends on patients’ adherence to the intended application use and daily reporting. Mild exacerbations may therefore be under-reported (but also over-reported in case of erroneous entries).
- Participants may not adhere to the intended constant wearing or charging regimens of the device and therefore available data may have too many gaps to allow meaningful interpretation.

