### 3.4.4 Handling of missing data

For variables obtained only at the baseline visit, missing values will not be replaced.

For the self-reported satisfaction questionnaire items, collected at the end of study visit, missing values will not be replaced. For variables measured daily during the observation period such as sensor-generated data, CAT score, and labelling information, missing data will not be imputed for all descriptive statistical analyses performed. The CAT score and derived sensor variables may be imputed for the purpose of building machine learning models if needed to avoid loss of instances using a suitable imputation method (e.g., LOCF, Forward filling, multiple imputation [MI], recursive imputation, median imputation). Sensitivity analyses will be conducted to assess the impact of imputation.

For variables with values collected at baseline, at the exacerbation visit and at end of study visit, missing values will not be imputed for all descriptive statistical analyses. Lung function parameters and lab values may be imputed for the purpose of building machine learning models if needed to avoid loss of instances by LOCF method if the last (previous) available value is recorded within 2 weeks before the date of the visit of interest. In cases where no value for a variable is available for a participant, imputation strategies across instances may be used (e.g., median imputation or iterative imputation methods). Sensitivity analyses will be conducted to assess the impact of imputation.

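### The two-weekly check against 18 exacerbations counts recorded events and does not ask whether sensor data exist before onset, so it can look satisfied with fewer than 18 usable events

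*Protocol*

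**What the plan says.** Protocol 9.5 derives the event target. It starts from "Assuming a desirable sensitivity and specificity of 0.85 for our algorithm", adds the condition "requiring that the lower 95% confidence limit should be at least 0.50 (with a probability of 0.95"), and concludes that "the number of observed exacerbation events needed is 18". At 0.5 events per participant in three months, 60 participants give a Poisson mean of 30 events; a 10% drop-out allowance raises enrolment to 67.

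Protocol 9.10.3 carries the target into study conduct: "Recruitment rates and exacerbation frequency in the COPD study population will be reviewed in 2-week intervals". The purpose is to allow adjustments in time "to reach the projected minimum number of moderate or severe exacerbations (n=18").

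Protocol section 7 states what the model needs. The start of an exacerbation, "regardless of how many exacerbations the patient may have experienced before, will be predicted based on sensor data preceding the" exacerbation. Moderate and severe events are recorded in the eCRF (Protocol 9.1.2.1), independently of the patch.

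Protocol 9.9 recognises that, because of poor wearing or charging, "available data may have too many gaps to allow meaningful interpretation". SAP 3.4.4 says that the CAT score and derived sensor variables "may be imputed for the purpose of building machine learning models if needed to avoid loss of instances", with last observation carried forward and forward filling among the example methods. Carry-forward of lung function and laboratory values is limited to two weeks; no limit is given for sensor variables. The COPD analysis set (Protocol 9.7.1, SAP 3.2) requires no minimum amount of sensor data.

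**The concern.** The count and the model draw on different data streams. An exacerbation enters the eCRF whether or not the patch was recording, but it is a real positive for Primary Objective 2 only if there is a sensor record before onset. As 9.10.3 is written, an event with no recording in the preceding days adds one to the comparison with 18, just as a fully recorded event does.

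The review exists to reveal a shortfall while something can still be done. If it follows all events while precision depends on usable ones, a shortfall of usable positives may come to light only at analysis. The drop-out allowance does not cover this, because it makes no provision for non-wear among participants who stay in the study.

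**Working it through.** **1. Reproduce the 18.** Inputs from Protocol 9.5: true sensitivity 0.85, lower 95% limit at least 0.50, assurance 0.95. The sidedness of the limit is not stated. With an exact (Clopper-Pearson) one-sided limit, the condition is met when the number detected, x, satisfies P(X ≥ x | n, 0.5) ≤ 0.05. For n = 18 this requires x ≥ 13, since P(X ≥ 13 | 18, 0.5) = 12616/262144 = 0.048. Then P(X ≥ 13 | 18, 0.85) = 0.958, so 18 is reproduced. A two-sided 95% limit would need 23 (assurance 0.954), so the plan's figure corresponds to a one-sided limit.

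**2. Assurance below 18** (one-sided exact limit):

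| Usable events | Detections needed | Assurance |
|---|---|---|
| 18 | 13 | 0.958 |
| 17 | 13 | 0.901 |
| 16 | 12 | 0.921 |
| 15 | 12 | 0.823 |
| 14 | 11 | 0.853 |

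The values are not monotone, because the required number of detections moves in whole steps. No n below 18 reaches 0.95; the maximum is 0.921, at 16. Just above 18 the curve also dips (0.946 at 19, 0.933 at 20), and it stays above 0.95 from 21 on. So 18 is the smallest n that meets the criterion and leaves no slack at the target itself.

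**3. Reproduce the participant numbers.** P(X ≥ 18 | Poisson mean 30) = 0.993; 30/0.5 = 60; 60/0.90 = 66.7, rounded up to 67. These agree with the plan.

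**4. Effect of a usable share u.** Neither document gives u, so what follows rests on assumptions: onsets uniform over 91 days, a lead-in of L days required, and a fraction w of events lost to non-wear independently of timing. Then u = (1 − L/91)(1 − w), and usable events are Poisson with mean 30u.

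| Lead-in L | Non-wear w | u | Mean usable | P(≥ 18 usable) | Usable if 18 are counted |
|---|---|---|---|---|---|
| 0 | 0 | 1.00 | 30.0 | 0.993 | 18.0 |
| 0 | 10% | 0.90 | 27.0 | 0.973 | 16.2 |
| 7 | 0 | 0.923 | 27.7 | 0.980 | 16.6 |
| 14 | 0 | 0.846 | 25.4 | 0.948 | 15.2 |
| 0 | 20% | 0.80 | 24.0 | 0.913 | 14.4 |
| 0 | 30% | 0.70 | 21.0 | 0.773 | 12.6 |
| 14 | 30% | 0.592 | 17.8 | 0.510 | 10.7 |

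The last column is the average number of usable events behind a review that shows exactly 18.

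**The case against.** Several points count against a stronger reading, and most of them stand.

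- A reader might infer that 18 is a trigger or stopping point. It is not. Protocol 9.10.3 calls it a projected minimum that guides adjustments, enrolment is planned at 67, and 30 events are expected. That margin absorbs moderate loss: at 90% usable the probability is still 0.97. The mean of 30 also ignores the seven participants allowed for drop-out. If each contributed half of follow-up (an assumption), the mean would be 30 + 7 × 0.25 = 31.75, and 85% usable would give 31.75 × 0.85 = 27.0 and a probability of 0.97.
- A reader might infer that the protocol expressly counts events in participants who have stopped wearing the patch or have just enrolled. It does not say so. It is silent, and the monitoring plan, which is not available here, may contain a working rule.
- A reader might infer that about 15% of events (14/91) are lost because they start too early. That needs a full 14-day lead-in, which nothing requires of the model. The 14-day windows in SAP 3.4.5.1 are descriptive, and Protocol 9.7.2.1 leaves the prediction period to be explored. With 7 days the loss is 7/91 = 8%.
- A reader might infer that empty windows will be filled with stable carried-forward values and that this lowers sensitivity. SAP 3.4.4 only permits imputation where needed, names multiple imputation among the options, and commits to sensitivity analyses. The direction of any bias is conjecture.
- Quoting only the fall from 0.958 at 18 to 0.823 at 15 would overstate the effect, because 15 is a local low point of an irregular curve.

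There are also safeguards: reminders and a compliance dashboard, a help line, withdrawal for unreliable device data (9.2.5), ongoing review of sensor data quality (9.7.3) and device replacement (9.10.6). They reduce the loss, but none is linked to the comparison with 18. Nor does the SAP 3.4.6 sensitivity analysis close the gap: it selects variables by missing rate, not events by whether their pre-onset window was recorded.

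**Conclusion.** The point holds in a limited form. The review in 9.10.3 follows recorded exacerbations, while the precision requirement in 9.5 needs exacerbations with pre-onset sensor data, and nothing in either document connects the two. The minimum can therefore appear reached with fewer than 18 usable events.

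If events arrive as planned, the consequence is small to moderate: the probability of at least 18 usable events is 0.98 with a 7-day lead-in and 0.95 with 14 days, and falls to 0.91 and 0.77 only if 20% or 30% of events are unusable. The problem matters more if events run below the 30 expected, because the margin is then gone and every number below 18 misses the stated 0.95 assurance. All usable shares here are assumptions, as are the uniform timing of onsets and the independence of non-wear. The study is declared exploratory, which lowers the stakes but does not make the count the right one to follow.

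**What to change.** In Protocol 9.10.3, compare 18 with evaluable events: moderate or severe exacerbations with non-imputed sensor data on a pre-specified minimum number of days before onset, for example 7 of the preceding 14. Show all events and evaluable events side by side at each two-weekly review.

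In SAP 3.4.4 and 3.4.5.2, state that a pre-onset window with no recorded data will not be imputed, set a limit in advance on how far sensor values may be carried forward (as already exists for lung function and laboratory values), and report sensitivity with the number of evaluable events as its denominator.

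No new data collection is needed, since sensor data are already under continuous review (Protocol 9.7.3). The cost is a short definition, a second column in the review, and an event count that looks somewhat less favourable.

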9.10.4 Health Authorities

The study must not start at a site before the protocol and any applicable documentation has been notified to the German Federal Institute for Drugs and Medical Devices (BfArM) in accordance with the § 47 (2) No. 2 and § 53 Section 1 MPDG.

In accordance with § 54 MPDG, all changes to the protocol and any applicable documentation will be notified to BfArM immediately.

In case of temporary suspension or premature termination of the study BfArM will be notified within 15 days with indications of the reasons. If the temporary suspension or premature termination are performed out of security reasons, the BfArM will be notified within 24 hours in accordance with §64 MPDG.

9.10.5 Quality Assurance

In compliance with regulatory requirements, the Sponsor, a third party on behalf of the Sponsor, competent authorities, or IRB/IECs may conduct quality assurance audits/inspections at any time during or following a study. The Investigator must agree to allow auditors/inspectors direct access to all study-related documents, including source documents, and must agree to allocate his or her time and the time of his or her study staff to the auditors/inspectors in order to discuss findings and issues.

The protocol, each step of the data capture procedure, and the handling of the data, as well as the study report, may be subject to independent Clinical Quality Assurance. Audits may be conducted at any time during or after the study to ensure the validity and integrity of the study data.

9.10.6 Medical Device Supply, Accountability and Handling

The Medical Device will be shipped by the manufacturer to the CRO and subjected to a receiving inspection. After successful receiving inspection the Medical Devices will be equipped with an ID, tracked and stored at the CRO in a restricted area. Only designated personnel involved in the supply chain of the Medical Devices will have access. The Medical Devices will be prepared for shipment to the sites by the CRO and tracked after handover to the logistic company.

The site will confirm the intact receipt of the Medical Device shipment in writing to the CRO. All Medical Devices must be stored in accordance with the manufacturer instructions. The investigator is responsible for assurance of adequate storage. The Device must be stored in a lockable room or locker, so that only investigator and specifically designated study personnel can have access. Only participants enrolled in the study may receive the devices and only authorized site staff may supply the device.

At the end of the study, all Medical Devices will be returned by the participants and checked for completeness at the site. Those devices and unused devices are returned to the CRO. The CRO will check, store and return the Medical Devices to the manufacturer.

Storage, dispensing and return of Medical Devices must be documented by the site and the CRO.

In case of reported device deficiencies, including malfunction, usability issues, or inadequacy in the information supplied by the manufacturer including labelling, the devices will be returned to the CRO, if already supplied, and the sponsor will be informed. Poorly performing devices will be replaced during the study and returned to the CRO by the site.

The study team at the CRO and site staff involved in the supply chain will be trained on the process.

9.10.7 Archiving

The archive should be maintained for the period specified by local regulations (10 years in Germany) (MPDG/appendix XV EU-MDR). All original participant files (medical records) must be stored at the site (hospital, research institute, or practice) for the longest possible time permitted

by the applicable regulations. In any case, the Investigator should ensure that no destruction of medical records is performed without the written approval of the Sponsor.

10 Protection of Human Participants

The sponsor will use safeguards to comply with national and European Union requirements for protecting the well-being and rights of human participants. To ensure the protection of privacy of participants, the sponsor is using data which have been pre anonymized and have had all protected health information removed. The sponsor will have no access to these data and will be unable to link these data to or identify the participants of the study. The sponsor will also restrict the access to the data to ensure that only those study personnel who have been appropriately trained and are in compliance with all of Merck's Codes of Ethics can examine the data.

